Clinical study protocol

Project Name: A prospective, single-arm, phase II clinical study of selmetinib hydrosulphate capsules for treating postoperative patients with neurofibromatosis type I

Sponsor: Sun Yat-sen Memorial Hospital of Sun Yat-sen University

Version number: V2.0

Version date: 2024.04.17

Project leader: [name]

Scheme signature confirmation:

Compliance Statement

In accordance with the provisions of the Good Clinical Practice for Drug Clinical Trials and the Administrative Measures for Clinical Studies initiated by Medical Institutions (Trial) and the Declaration of Helsinki, we promise to carry out this study according to this protocol. The participants must be trained to conduct the study after the written approval of the Ethics Committee and the written informed consent of the subjects, and the protocol revision shall be re-approved again.

1. Protocol abstract (title, brief description of study, study object, outcome measures, study intervention*, Sample size, etc., in 300–500 words)

This study focuses on patients with neurofibromatosis type I, who lack effective medical therapy and has a high recurrence rate after surgical resection. For patients with small solid tumors, limited space occupying, and not invading the brain, spine and other important organs, surgical treatment is the main treatment means. As a MEK inhibitor, by selectively binding the mitogen-activated protein kinase (MEK) 1 / 2 protein, it can block the mitogen-activated protein kinase / extracellular signal-regulated kinase signaling pathway that regulates key cellular responses, and can induce tumor shrinkage and reduce postoperative recurrence. The purpose of this study is to treat hydrosulphate for patients with surgical indications, to observe the efficacy of drug treatment, consolidate the postoperative efficacy and reduce the recurrence rate. In this study, progression-free survival (PFS) after drug treatment was used as the main study outcome measure, duration of remission (DOR) and objective response rate (ORR) as secondary outcome measures to explore the use of selmetinib sulphate for tumor control efficacy, reduction of recurrence rate, and stability of efficacy in patients with neurofibromatosis type I.

2. Introduction (references to be noted in the introduction)

2. 1 Research theoretical basis / background (explain why clinical studies are conducted from the limitations of disease, standard of treatment and known treatment, and explain the findings and importance of preclinical, pharmacological and related studies)

Neurofibromatosis (NF) has been included in the list of rare diseases in many countries including China, 96% of which are NF 1 subtypes, and

the clinical manifestations of NF 1 are diverse^[1], involving multiple systems and can cause serious complications such as airway obstruction, spinal cord compression and motor dysfunction^[2-4]. Plexiform neurofibromas (PN) occur in 30 to 50% of NF 1 patients^[5, 6], PN progress fast, accompanied by serious appearance defects, high disability, and the risk of deterioration^[7-10]. According to the 2023 edition of the multidisciplinary diagnosis and treatment of type I neurofibromatosis, patients with NF 1 are more likely to have a variety of benign and malignant tumors than the normal population, including pNF, CNF, MPNST and OPG. Attention should be paid to the early identification and monitoring of the above tumors. Neurofibromas with accelerated growth, pain and hard texture. At the same time, systemic evaluation should be carried out, and patients with no signs of distant metastasis should undergo early surgical treatment as far as possible, and patients with distant metastasis can choose radiotherapy, chemotherapy and targeted therapy.

Neurofibromatosis type I (neurofibromatosis type 1, NF 1) is an autosomal dominant disorder with 50% of patients with familial and 50% sporadic mutations. NF 1 gene encodes neurofibromin, downregulates the activity of Ras-Raf pathway and suppresses cell proliferation; deficiency in neurofibrosis causes excessive activation of RAS pathway and causes uncontrolled cell proliferation in NF 1 patients^[5]. At present stage, surgery is the most commonly used, the main treatment, and neurofibroma has the characteristics of the nerve root growth, it is difficult to solve all lesions through surgery, lesions composed of extensive nerve and vascular tissue and normal tissue, surgical resection difficult and bleeding, incomplete resection after recurrence as high as 50%. NF 1 occurs in the head and neck. Some patients need secondary surgery 1 year after surgery, and the proportion of patients with partial resection after secondary surgery is higher than that of patients with subtotal resection.

Five years after surgery, the proportion of secondary surgery was more than 50%^[7]。

As a MEK inhibitor, it blocks the mitogen-activated protein kinase / extracellular signal-regulated kinase signaling pathway by selectively binding to the mitogen-activated protein kinase (MEK) 1 / 2 proteins that regulate key cellular responses^[11-13], And then induce tumor shrinkage, creating conditions for disease control, surgical resection, reducing postoperative recurrence and reducing complications. Based on the targeted treatment of hydrogen sulphate smetinib capsule, this study for NF 1 patients, evaluated after enrollment, after the patients with tumor monitoring solid tumor shrinkage effect and the duration of efficacy, and postoperative recurrence time, and then verify the effectiveness of hydrosulphate smetinib capsule to reduce the recurrence rate of NF 1 patients.

2.2 Risk / benefit evaluation

2.2.1 Known potential risks

The potential risks of this study are mainly the adverse reactions after the use of selmetinib hydrosulphate capsules, the hyperprogression of tumor treatment caused by the study protocol itself, and the risk of sudden accidents in the study.

2.2.2 Known potential benefits

The potential benefit of the subjects in this study enables the subjects to achieve partial tumor remission, delay progression, reduce recurrence, and improve function; entering the clinical study can gain more attention from the investigators and handle the disease changes in time, which is beneficial to the treatment of the disease.

2.2.3 Potential risk and benefit evaluation

Smetinib Insulphate capsule is indicated for pediatric patients with

neurofibromatosis type I (NF 1) aged 3 years and older with symptomatic, inoperable plexiform neurofibromas (PN). It was approved to list in China on April 28, 2023, and was included in the medical insurance directory on December 13, 2023. Several guidelines, consensus and diagnosis and treatment norms in China recommend selmetinib hydrohydrogen sulfate for the treatment of NF 1-PN. The most common toxicity of selmetinib hydrosulphate capsules is grade 1 and 2 gastrointestinal symptoms (nausea, vomiting, or diarrhea), asymptomatic elevated creatine phosphokinase levels, acne-like rash, and paronychia with good safety and tolerability. Therefore, this clinical study protocol has a low risk of disease progression and serious adverse events on the treatment of NF 1^[14, 15]. At the same time, in the future studies, the investigators will pay more attention to the subjects' systemic condition and tumor treatment condition, and the subjects will also gain some clinical benefit in this study.

3. Study objective and endpoint (list presentation objective (specific issues to be addressed), corresponding to the outcome measures)

3.1 Purpose

3.1.1 Main Purpose

The primary objective of this study is to explore the progression-free survival (PFS) after 6 cycles of selmetinib hydrosulphate capsules in patients with neurofibromatosis type I (NF 1).

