3.2.1 Main Indicators and Definitions

2-year progression-free survival rate (2-year PFS rate): the rate of no tumor progression or death from any cause within 2 years from postoperative treatment (whichever comes first).

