5.2 Study design process

5.2.1 Study the specific implementation process

This study started from the recruitment of subjects, with clinical diagnosis, definite diagnosis by pathological biopsy, primary screening according to inclusion criteria and exclusion criteria, and signed informed consent before enrollment. After evaluation as indication for surgical resection and surgical treatment, selmetinib hydrosulphate capsules. PFS, ORR and DOR were assessed after 6 cycles of oral selhydrosulphate capsules (20–50mg bid).

Demographic data	✓										
medical history	✓				✓			✓	✓	✓	✓
ECOG grade	✓	✓	✓	✓	✓	✓	✓	✓	✓	✓	✓
check-up	✓	✓	✓	✓	✓	✓	✓	✓	✓	✓	✓
vital sign	✓	✓	✓	✓	✓	✓	✓	✓	✓	✓	✓
electrocardiogram	✓				✓			✓	✓	✓	✓
routine blood test	✓		✓	✓	✓	✓	✓	✓	✓	✓	✓
Blood biochemical	✓		✓	✓	✓	✓	✓	✓	✓	✓	✓
Liver, kidney, and cardiac function	✓		✓	✓	✓	✓	✓	✓	✓	✓	✓
coagulation function	✓		✓	✓	✓	✓	✓	✓	✓	✓	✓
Heart ultrasound	✓				✓			✓	✓	✓	✓
Pathological biopsy	✓										
Infectious disease examination (hepatitis B, hepatitis C, HIV, syphilis)	✓										
Imaging examination	✓				✓			✓	✓	✓	✓
complication And adverse event assessment			✓	✓	✓	✓	✓	✓	✓	✓	✓

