5.4 Definition of end of study (e. g. last subject completes last follow-up)

5.5 Statistical analysis

5.5.1 Sample size and basis for calculation

The estimated sample size was based on the objective response rate. The hypothesis of this study is that selmetinib sulphate can reduce the recurrence rate of patients after NF 1. The study parameters were set: $\alpha = 0.025$ (unilateral), Power=80%, and progression-free survival (PFS) in 20% of patients with NF 1 for 24 months. More than 50% of progression-free survival (PFS) in NF 1 patients. 17 cases were calculated using PASS 15.0 software, considering 10% shedding rate, 19 subjects should be included.

.5.52 Data analysis set (e. g. full analysis set, compliance protocol set, safety analysis set)

Statistical analysis will be performed using the SAS statistical software (V. 9.4, SAS Institute) Statistical analysis software for calculation, if no special instructions, the main indicators use one-sided test, control the first class error α is 0.025, the remaining indicators use two-sided test, one class error is $\alpha = 0.05$. To calculate confidence intervals, calculate two-sided 95% confidence intervals if not otherwise specified.

(1) Full analysis set (full analysis set, FAS): consisting of all subjects who received at least one drug / treatment and obtained efficacy assessment. This dataset was derived from all subjects after removing subjects in the least and reasonable way.

(2) Safety analysis set (safety analysis set, SS): a population treated at least once / once and having at least one safety evaluation data. In the safety analysis, all patients will be analyzed by the actual drug group.

(3) Compliance with the protocol set (per-protocol set, PPS): all concomitant medications that met the trial protocol and did not use the

impact effectiveness evaluation, good medication compliance (between 80% and 120%), excluded subjects who had major protocol violations and were judged to have a significant impact on the results. All protocol deviations causing the exclusion of subjects from the compliant protocol set will be described in detail in the Statistical Analysis Plan (SAP) and completed prior to data lock.

5.3 5 Statistical analysis plan

Data description of statistical analysis, analysis method of primary / secondary indicators / safety indicators, statistical school positive method, control of bias, stratification / subgroup / sensitivity analysis, etc

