Main index analysis adopts LOCF (last observation carried forward) method, that is, the main index data is not observed at the last time; the secondary indicators and safety indicators are not filled.

6. Research intervention*

6.1 Study intervention content (description of intervention content, implementation steps, dose and route of intervention drug, frequency of intervention, product of test group and control group, etc.)

All patients received oral selmetinib hydrosulphate capsules (20–50mg bid) daily for 30 days for 6 cycles, based on individualized patient body surface area (BSA).

6.2 Preparation / handling / storage / responsibilities (drug versus control article allocation plan when intervention should be specified)

The use of drugs must be recorded in the patient's medical record and in the corresponding location of the CRF. After the enrollment of the subjects and at the 1 and 2 months of follow-up, the executive nurse shall receive the corresponding number of drugs at the drug administrator, and the remaining drugs and boxes shall be returned to the drug administrator. If the drug is found or damaged during the preparation process, this box of drugs should not be used, the damaged drugs shall be treated as empty bottles, and other undamaged drugs shall be returned to the drug administrator together with the packaging box. The study center shall be responsible for the management of test drugs, including receiving, distribution, counting and recovery. The investigator shall ensure that the test drug is stored in a safe, independent and locked place at the study site and the storage conditions shall meet the storage requirements of the test drug. No one can be contacted without the consent of the investigator. Empty boxes shall be stored and managed as the test drug.

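### The time zero for primary PFS is inconsistent (after six cycles, or from postoperative treatment), and the 20% benchmark has no stated origin

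*Protocol*

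**What the plan says.** The protocol words the start of PFS differently in different places.

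- Section 1 (abstract): "progression-free survival (PFS) after drug treatment was used as the main study outcome measure". This could mean from the start of drug or from its end.
- Section 3.1.1 (primary objective): to "explore the progression-free survival (PFS) after 6 cycles of selmetinib hydrosulphate capsules".
- Section 3.2.1 (formal definition of the main indicator): "the rate of no tumor progression or death from any cause within 2 years from postoperative treatment".
- Section 5.2.1 (process): "PFS, ORR and DOR were assessed after 6 cycles of oral selhydrosulphate capsules".

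Section 6.1 gives the length of the regimen, "daily for 30 days for 6 cycles", so six cycles take 6 × 30 = 180 days, about six months.

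The rates for the test are in section 5.5.1. The null is given as "unilateral), Power=80%, and progression-free survival (PFS) in 20% of patients with NF 1 for 24 months" and the target as "More than 50% of progression-free survival (PFS) in NF 1 patients". Neither sentence says when the 24 months begin. The same section gives 17 subjects, raised to 19 for 10% dropout. The efficacy analysis uses a Clopper-Pearson interval, with success declared if its lower limit exceeds the historical proportion.

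**The concern.** The primary result is a single proportion set against a fixed historical number, so the start of the clock determines who counts as a failure. Section 3.1.1 can be read as starting PFS once six cycles are finished. Section 3.2.1 starts it at postoperative treatment. These differ by about 180 days of a 24-month endpoint. Section 3.2.1 is itself open, because postoperative treatment could refer to the operation or to the first dose after it, and section 5.2.1 does not give the interval between the two.

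No section says in so many words whether a progression during the six cycles is a primary-endpoint event. If it is not, the analysis conditions on having stayed progression-free through treatment. If the 24 months run from the end of cycle 6 with earlier events kept, the rate is really read at month 30. Two analysts following different sections could reach different conclusions from the same 19 subjects, and the choice could be made after outcomes are known.

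**Working it through.** **Inputs from the protocol.** Null rate p0 = 0.20 and target p1 = 0.50 at 24 months, one-sided α = 0.025, power 80%, n = 17 and 19 (section 5.5.1); six cycles = 180 days ≈ 6 months (section 6.1). **Assumption, not in the protocol:** a progression curve. I use constant hazard, then Weibull curves of shape 0.5 to 2 through the same 24-month rate.

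**1. The plan's own sample size.** Normal approximation for one proportion:

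n = [(1.960·√(0.2·0.8) + 0.842·√(0.5·0.5)) / 0.3]² = 16.13, rounded up to 17; 17/0.9 = 18.9, so 19. The stated figures reproduce.

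**2. Decision rule with one origin.** I read the criterion as the lower limit of the two-sided 95% Clopper-Pearson interval exceeding 20%, which matches the stated one-sided α. At 8 successes the lower limit is 0.230 (n=17) and 0.2025 (n=19). At 7 it is below 0.20 for both. Success therefore needs at least 8.

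| n | P(X≥8 at 0.20) | P(X≥8 at 0.50) |
|---|---|---|
| 17 | 1.09% | 68.5% |
| 19 | 2.33% | 82.0% |

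**3. Reading A: progressions in months 0–6 not counted, 24-month mark kept.** Constant hazard with S(24) = 0.20 gives S(6) = 0.20^(6/24) = 0.669. The apparent null rate is S(24)/S(6) = 0.20/0.669 = 0.299.

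- *Early progressors leave the denominator.* The number remaining is binomial with probability 0.669 (on average 0.669 × 19 ≈ 12.7 of 19). Reapplying the Clopper-Pearson rule to each possible number and averaging gives a type I error of 8.1% (start 17) or 8.8% (start 19).
- *All 17 or 19 analysed subjects are progression-free at month 6.* P(X≥8 at 0.299) = 10.3% (n=17) or 18.0% (n=19). Over Weibull shapes 2 to 0.5 the range is 2.0% to 51.6% at n=17 and 4.1% to 67.4% at n=19.

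**4. Reading B: the whole 24-month clock restarts after cycle 6 among those still progression-free.** The null rate is S(30)/S(6). Under constant hazard this is 0.20^(24/24) = 0.20, so with 17 or 19 such subjects type I error stays at 1.09% or 2.33%. At n=17 it rises if the hazard falls over time (shape 0.75: 5.4%; shape 0.5: 26.7%) and drops if the hazard increases (shape 1.5: 0.06%).

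**5. Reading C: 24 months from the end of cycle 6, early events kept.** The rate is read at month 30. A true 24-month rate of 50% becomes 0.50^(30/24) = 0.420, and P(X≥8 | 19, 0.420) = 58.5%, against 82.0% in step 2. Over shapes 0.5 to 2 it runs from 71.6% to 29.6%. A 20% null becomes 0.20^(30/24) = 0.134, so false success becomes less likely.

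**The case against.** The best defence is that section 3.2.1 is the only place that gives event, window and origin together, and it excludes no on-treatment progression. Section 3.1.1 may use six cycles simply to name the regimen. Section 5.2.1 covers ORR and DOR in the same sentence and may describe when outcomes are assessed. The full analysis set takes anyone treated with an efficacy assessment, so a subject who progresses in cycle 3 and was assessed belongs in it. No section limits the analysis to those who complete six cycles.

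Much of this stands, and it rules out several stronger readings that a reader might infer:

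- *Three separate time origins.* There are several wordings but only two clearly distinct origins. The abstract's phrase can coincide with either.
- *The plan drops early progressors.* It does not say so. Reading A is something the wording permits, not something it prescribes.
- *Type I error of 18.0% as the expected size.* That figure applies a rate among month-6 survivors to a full 19. It would need 19 subjects progression-free at month 6, and no section provides for replacing early progressors.
- *Inflation as a general consequence.* Reading B gives none under constant hazard, and Reading C costs power instead.
- *A demonstrated mismatch with the historical rate.* The 20% has no stated origin, so neither a match nor a mismatch can be shown.

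The defence does not remove the conflict itself. The benign reading of section 3.1.1 is nowhere stated, the definition leaves surgery or first dose open, and the benchmark is undated. The objective and the definition are both protocol text, so a later analysis plan could follow only one reading of them.

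**Conclusion.** The point holds as an inconsistency in the primary endpoint's time zero, chiefly between sections 3.1.1 and 3.2.1, together with an undated benchmark. It needs settling before any outcome is read.

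Its numerical effect is conditional. Under constant hazard, not counting the first six months' progressions while keeping the 24-month mark puts type I error at about 8% to 9% when early progressors leave the denominator. The 10.3% and 18.0% figures apply only if all 17 or 19 analysed subjects are progression-free at month 6. A clean restart of the clock leaves type I error unchanged under constant hazard, and reading the rate at month 30 with early events kept lowers power. The protocol gives no progression curve, and the wide Weibull ranges show how far the size rests on that assumption. With one origin and all events counted, the exact type I error is within 2.5% at both sample sizes, provided the 20% benchmark refers to that same origin.

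**What to change.** Use one time zero in sections 1, 3.1.1, 3.2.1 and 5.2.1, for example the date of the first postoperative dose, which fits section 3.2.1. State that every progression or death from that date counts, including during the six cycles, and that the rate is read at 24 months from it. Let the reference to six cycles describe only the regimen or the timing of an assessment. In section 5.5.1, state the origin of the 20% rate and justify it from the same time zero. If its source counts from a different point, say so and address the difference.

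The cost is protocol wording, plus checking the source of the benchmark; no extra data are needed. The downside is that the reported rate may be lower than under a reading that leaves out on-treatment progressions, because they now count.

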3.1.2 Secondary Purpose

The secondary objective of this study is to explore the duration of remission (DOR) and objective response rate (ORR) in postoperative patients with neurofibromatosis type I (NF 1).

3.1.3 Exploratory Purpose

The exploratory purpose of this study is to explore the long-term

efficacy and stability of patients with neurofibromatosis type I (NF 1) treated with selmeteitinib capsules.

3.2. study indicators

3.2.1 Main Indicators and Definitions

2-year progression-free survival rate (2-year PFS rate): the rate of no tumor progression or death from any cause within 2 years from postoperative treatment (whichever comes first).

3.2.2 Secondary indicators and Definitions

Duration of response (DOR): the time between the start of CR or PR and the first assessment of PD or death from any cause.

Objective response rate (ORR): the proportion of patients with a 20% tumor reduction for a certain period of time, including complete response (CR) and partial response (PR). The ORR was defined as the proportion of patients with a 20% tumor size reduction in the shortest time period.

3.2.3. safety indicators

The subject's vital signs, blood routine, liver function, blood biochemistry, urine routine, stool routine, coagulation function, left ventricular ejection fraction (LVEF), creatine phosphokinase, vitamin E, and bleeding risk.

4. study population

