4.1 Inclusion criteria

- (1) Age ≥ 18 years old
- (2) According to the updated NF 1 diagnostic criteria of the National Institutes of Health (NIH) in 2021,
 - ① 6 or more CALMs: $d > 5$ mm before puberty or $d > 15$ mm after puberty;

② 2 or more neurofibromas of any type or 1 plexiform neurofibroma;

③ Plaques in the axillary or inguinal area;

④ Optic glioma (OPG);

⑤ Slit lamp examination of two or more Lisch nodules, or optical coherence tomography (OCT) / imaging of two or more near infrared (NIR) choroid abnormalities;

⑥ Characteristic bone lesions, such as sphenoid dysplasia and anterolateral curvature of the tibia;

⑦ Pathogenic heterozygous NF 1 variants with allelic variant scores of 50% in normal tissues (such as leukocytes);

Patients with no parental history and fulfilling 2 or more clinical characteristics could be diagnosed with NF 1

Parents with a history of 1 or more clinical features can be diagnosed with NF 1

(3) Before enrollment, a head and neck surgeon performed a pathological biopsy of the solid tumor to clarify the pathological diagnosis and exclude the malignant peripheral schwannoma (MPNST)

(4) At least one measurable tumor lesion according to the efficacy evaluation criteria of solid tumors RECIST 1.1

(5) The tumor did not invade the brain, spine and other important organs, and there are indications for surgical resection and surgical treatment

(6) The performance status of the Eastern Cooperative Oncology Group (Eastern Cooperative Oncology Group, ECOG) was 0-1

(7) Blood routine: white blood cell count (WBC) 3.010^9 / L; Absolute neutrophil count (ANC) 1.510^9 / L; Platelet (PLT) 10010^9 / L; hemoglobin level (HGB) 9.0 g/dL (no corresponding supportive care, such as transfusion and increased leukocytes within 7 days).

(8) Liver function: 2.5 times aspartate aminotransferase (AST) and alanine aminotransferase (ALT); albumin (ALB) 30 g / L.

(9) Renal function: serum creatinine 1.5 times ULN or creatinine clearance (CrCl) 50 mL/min (using the Cockcroft / Galt formula); urinary protein (UPRO) <(+ +), or 24-hour urinary protein <1.0 g.

(10) Cardiac function: blood creatine phosphokinase 200U / L, left ventricular ejection fraction (LVEF) 50%;

(11) Did not participate in other clinical trials within the previous 30 days;

(12) Patients who voluntarily participate in the project and sign the informed consent form.

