5.1 Overall design (including assumptions, type, etc.)

This study hypothesized that selmetinib hydroxyl sulphate capsules are effective in neurofibromatosis type I, including improving efficacy after tumor resection, delaying progression, reducing recurrence, and improving function. The prospective, single-arm, phase-study study protocol was designed to estimate progression-free survival (PFS) in more than 50% of NF 1 patients at 24 months, objective response rate (ORR) of 40%, and duration of tumor response (DOR) of 12 months.

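### The two ORR sentences in Protocol 3.2.2 are not equivalent and leave the 20% threshold without a measure, so the responder count and entry into DOR are not fixed

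*Protocol*

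**What the plan says.** Protocol 3.2.2 gives ORR first as "the proportion of patients with a 20% tumor reduction for a certain period of time, including complete response (CR) and partial response (PR"). The next sentence defines it again: "The ORR was defined as the proportion of patients with a 20% tumor size reduction in the shortest time period".

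The same section measures DOR as "the time between the start of CR or PR and the first assessment of PD or death from any cause". The protocol gives no criterion for partial or complete response apart from the 20% in the ORR text.

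The only named tumour criteria are in inclusion criterion 4 of section 4.1: "At least one measurable tumor lesion according to the efficacy evaluation criteria of solid tumors RECIST 1.1". That governs whether a lesion can be measured at entry, not what counts as a response.

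Section 5.1 attaches expectations to both endpoints: "objective response rate (ORR) of 40%, and duration of tumor response (DOR) of 12 months". Section 5.2.1 adds that "PFS, ORR and DOR were assessed after 6 cycles of oral selhydrosulphate capsules (20–50mg bid"), which does not say whether a response must persist or on what scale it is measured.

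**The concern.** A patient whose tumour is 20% smaller on one scan and has regrown by the next is a responder under the second sentence, read literally. Under the first, the same patient may not be one, depending on a duration that is not stated. A patient whose tumour has lost 20% of its volume is a responder if the 20% means volume, and well short of the threshold if it means diameter.

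DOR is calculated only in responders, so it inherits both uncertainties. ORR and DOR are the only named secondary endpoints. The trial has one arm, so a lenient definition is not offset by a control group judged in the same way. If the protocol leaves the rule open, it can be chosen after the scans have been read, and with about 19 patients a few borderline cases decide how the result compares with the expected 40%.

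**Working it through.** **Step 1. Set the two sentences side by side.**

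| Element | First ORR sentence | Second ORR sentence |
|---|---|---|
| Threshold | 20% | 20% |
| Time rule | must last, length not given | shortest period, no persistence as written |
| Link to CR and PR | yes | none |
| Diameter or volume | not stated | not stated (size only) |
| Baseline scan | not stated | not stated |

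The threshold agrees. The time rule does not, and three elements needed to classify a patient (duration, measure, baseline) are absent from both.

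**Step 2. What the missing measure does to the threshold.** Input: the 20% of section 3.2.2. Assumption: the tumour shrinks uniformly, so area scales with the square of diameter and volume with its cube.

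- 20% in diameter: area falls by 1 − 0.8² = 36.0%, volume by 1 − 0.8³ = 48.8%.
- 20% in area: diameter falls by 1 − 0.8^(1/2) = 10.6%, volume by 1 − 0.8^(3/2) = 28.4%.
- 20% in volume: diameter falls by 1 − 0.8^(1/3) = 7.2%, area by 1 − 0.8^(2/3) = 13.8%.

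The same written threshold can therefore mean a fall in diameter of anything from 7.2% to 20%, or a fall in volume of anything from 20% to 48.8%.

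**Step 3. What one patient is worth.** Input: 19 subjects (section 5.5.1). Each patient counted differently moves ORR by 1/19 = 5.3 percentage points.

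The expected 40% corresponds to 0.40 × 19 = 7.6, so about 8 responders. With the Clopper-Pearson two-sided 95% interval that the plan specifies for rates:

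| Responders of 19 | ORR | 95% interval |
|---|---|---|
| 6 | 31.6% | 12.6% to 56.6% |
| 8 | 42.1% | 20.3% to 66.5% |
| 10 | 52.6% | 28.9% to 75.6% |

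The shift of two patients either way is only an illustration. The documents do not allow the actual number to be derived.

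**Step 4. What happens to DOR.** The time rule decides which patients count as responders and so enter DOR. It does not move the start date of a patient who qualifies either way, since response begins at the first qualifying scan under both rules. The measure can move that date, because a threshold of 7.2% in diameter may be crossed at an earlier scan than one of 20%.

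**Step 5. Does the sample size depend on ORR?** Inputs from section 5.5.1: 24-month PFS of 20% against 50%, one-sided α = 0.025, power 80%. The normal approximation for one proportion gives

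n = [(1.960 × √(0.2 × 0.8) + 0.842 × √(0.5 × 0.5)) / 0.3]² = 16.13, rounded up to 17,

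and 17 / 0.9 = 18.9, rounded up to 19. The plan's 17 and 19 are reproduced from PFS rates alone, so no ORR figure enters.

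**The case against.** The best defence is that the document is a rough translation and that the second sentence was meant as a minimum-duration rule. The two sentences would then restate a single rule: a 20% reduction held for at least some minimum time. This is plausible, and a reader who infers that the protocol certainly contains two rival definitions goes further than the text allows. But even on this reading no duration is stated, so the rule still cannot be applied.

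A second defence is that measurement scale and confirmation can be left to the statistical analysis plan, which is not shown. That would hold if the protocol were silent. Instead it fixes the endpoint twice in different words, and an analysis plan that follows one sentence as written departs from the other. The missing measure alone would be a weaker point. It matters here because the 20% is the only response criterion the protocol gives.

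A third is that no decision rests on ORR. That is correct: it is secondary, reported as an estimate with an interval, and the 40% has no test or success rule attached.

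Two stronger inferences should also be resisted. Section 5.5.1 says "The estimated sample size was based on the objective response rate", which could suggest that the ambiguity undermines the sample size. The parameters that follow are PFS rates, so it does not; that mismatch is a separate matter. A reader might also use the 12-month DOR to estimate how far ORR would fall if responses had to be confirmed. The documents do not support this: DOR ends at progression or death, not when the 20% reduction is lost, and the imaging intervals cannot be read because the schedule's column headings are not available in the text at hand.

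**Conclusion.** The point stands as a defect in the wording of a secondary endpoint that should be corrected. The two sentences as written are not equivalent, neither gives a usable duration or measure, and nothing elsewhere in the protocol settles the matter. The responder count and membership of the DOR analysis depend on the sentence followed; the DOR start date can depend on the measure.

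The size that can be stated is the gap between the readings of the threshold (48.8% against 20% in volume, or 20% against 7.2% in diameter) and the weight of one patient at n = 19. The first rests on uniform shrinkage, the second on all 19 subjects being evaluable. How many patients would change class is unknown. The ORR wording does not enter the definition of the primary endpoint, the 2-year PFS rate, or the sample size.

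**What to change.** Delete the second ORR sentence in section 3.2.2 and state one rule:

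- A response is a reduction of at least 20% from a baseline scan that the protocol identifies.
- The reduction is in one named measure, and the same measure is used to judge progression.
- The reduction is still present at the next scheduled imaging.
- DOR starts at the first qualifying scan.
- A responder first seen at the final scan is counted as unconfirmed.

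The sponsor should choose the baseline scan and the measure before any response data are reviewed.

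The cost is a wording amendment. The schedule in section 5.2.1 marks imaging in its first column and in five later ones, so confirmation needs no added visits. The downside is that the confirmed ORR may be lower than an any-time ORR, by an amount the documents do not allow to be computed. The sponsor should therefore also say which of the two the expected 40% refers to.
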